3. PROTOCOL SYNOPSIS

Full Title	Control of COVID-19 outbreaks in long term care		
Short Title	CONTROL-COVID-1		
Protocol Number	CONTROL-COVID-Favipiravir-1		
Version Number and Date	Version 2.0, June 4, 2020		
Study Duration	Enrollment period: May 10, 2020 to Oct 31, 2020		
	Study period: April 1, 2020 to March 31, 2021		
Principal Investigator	[name]		
Number of Centers	60 screened, 16 enrolled		
Number of participants	Estimated: 760		
Study Design	Placebo-controlled cluster-randomized trial		
Primary Objective	Evaluate the efficacy of favipiravir chemoprophylaxis for control of outbreaks of COVID-19 in long-term care homes (LTCH).		
Secondary Objectives	To compare the following secondary outcomes between study arms:		
	1. The proportion of residents of included LTCH units who die up to day 40, and up to day 60		
	2. The proportion of residents of included LTCH units who were uninfected at baseline and develop new symptomatic microbiologically confirmed COVID-19 up to day 40		
	3. The proportion of exposed staff uninfected at baseline in whom SARS-CoV-2 infection is identified up to day		

	14 and up to day 40		
	4. The proportion of residents of included LTCH units hospitalized up to day 40		
	5. The proportion of residents of included LTCH units who discontinue study medication due to adverse events		
	6. The proportion of LTCH staff of included LTCH units who discontinue study medication due to adverse events.		
	7. The occurrence of new microbiologically confirmed COVID-19 infections in residents in other units of the facility up to day 40 (dichotomous, at LTCH level)		
	8. The proportion of previously unaffected LTCH units of the remainder of the facility in which a case of COVID-19 is identified		
	9. The proportion of residents in the remainder of the facility who develop COVID-19 infections up to day 40		
Sample Size	8 units per arm (16 units in total)		
Randomization	Cluster trial with probabilistic minimization		
Study Population	Residents and staff of LTCH for older adults, Ontario		
Investigational Product Description	Favipiravir 200 mg tablets		
Control	Placebo		
Administration and Dosing	Favipiravir 1600 mg orally twice daily on day one then 800 mg orally twice daily for prophylaxis, and 2000 mg orally twice daily on day one then 1000 mg orally twice daily for treatment		
Duration of Treatment	Starting once a COVID-19 outbreak in an LTCH unit (>=2 symptomatic microbiologically confirmed COVID-19 cases) has been identified and continuing until day 25		
Outcome Measures	Primary outcome:		
	Control of outbreak, defined as no new cases of COVID-19 in residents for 24 consecutive days up to day 40 after the		

	start of prophylaxis
	Secondary outcomes:
	1. The proportion of residents of included LTCH units who die up to day 40, and up to day 60
	2. The proportion of residents of included LTCH units who were uninfected at baseline and develop new symptomatic microbiologically confirmed COVID-19 up to day 40
	3. The proportion of exposed staff uninfected at baseline in whom SARS-CoV-2 infection is identified up to day 14 and up to day 40
	4. The proportion of residents of included LTCH units hospitalized up to day 40
	5. The proportion of residents of included LTCH units who discontinue study medication due to adverse events
	6. The proportion of LTCH staff of included LTCH units who discontinue study medication due to adverse events.
	7. The occurrence of new microbiologically confirmed COVID-19 infections in residents in other units of the facility up to day 40 (dichotomous, at LTCH level)
	8. The proportion of previously unaffected LTCH units of the remainder of the facility in which a case of COVID-19 is identified
	9. The proportion of residents in the remainder of the facility who develop COVID-19 infections up to day 40
Statistical Analysis	Primary outcome: Fisher's exact test (two-sided) comparing control of outbreak in homes receiving study drug versus placebo

4. INTRODUCTION, BACKGROUND, AND STUDY RATIONALE

4.1 Overview and Study Rationale

A novel coronavirus, SARS-CoV-2, emerged in December 2019 in Wuhan, China. 1,2 Causing a febrile respiratory illness known as COVID-19, this is the third zoonotic coronavirus of the past two decades to infect humans, after SARS-CoV and MERS-CoV. 3

COVID-19 is spreading far more rapidly than its predecessors, having infected over 2,300,000 persons worldwide as of April 18th.⁴ Rapid transmission has been fuelled by the high intrinsic reproductive number of 2-2.5,⁵⁻⁷ burgeoning community transmission,⁸⁻¹⁰ and the potential for occult transmission during the pre-symptomatic incubation period.¹¹⁻¹³

As the scale of the ongoing COVID-19 reaches pandemic proportions, intensive public health efforts are underway to control the outbreak. Governments have instituted travel bans, intensified airport screening, implemented case isolation, contact tracing and quarantine of atrisk contacts. While such interventions appear to have reduced the effective reproductive number, and slowed ongoing transmission within China, international cases continue to grow. Public health control measures such as symptomatic case-isolation and quarantine of at-risk patients may be insufficient to control the pandemic, particularly in light of evidence of transmission from minimally symptomatic or subclinical cases. 11,13,19

Canada was amongst the first countries outside of China to identify a case of COVID-19,²⁰ and has already begun to see rising case numbers.²¹ It is likely that continuing local transmission will result in on-going infection across the country.

In China, nearly one-fifth of infected patients experience severe or critical illness as a result of COVID-19, 22 with an overall 2.3% case fatality rate and up to 6.1% of patients experiencing severe complications (intensive care unit admission, invasive ventilation, or death). While patients across all age-categories have been infected by SARS-CoV-2, 22,24,25 the elderly are disproportionately bearing the consequences of this pandemic. Most patients dying are \geq 60 years of age, with case fatality rising drastically from 0.2% for individuals < 40 years of age to 14.8% for those \geq 80. 22

The first evidence of Canadian community transmission of SARS-CoV-2 was found in a nursing home in British Colombia, leading to the first death in Canada. Similarly, in the United States a significant outbreak has been reported in a Seattle-based nursing home. While guidelines and many preventive strategies have been implemented in long term care homes (LTCHs), an increasing number outbreaks are being reported in many countries, including across Canada. Given the structure of LTCHs, and the evidence of difficultly preventing outbreaks and limiting the spread of other respiratory viruses, it is highly likely that many outbreaks of COVID-19 will occur in LTCHs, with devastating consequences for residents and their families.

The long-term care population reflects a particularly frail and elderly subset of patients, with a median age of 86 years across Canada. Despite a significantly lower typical case fatality rates for influenza as compared to COVID-19, case fatality rates for influenza outbreaks in LTC facilities have been identified to be as high as 55%. ²⁹ Outbreaks of COVID-19 are escalating in Canadian LTCHs, with strikingly high case fatality rates. Residents of LTCHs comprise nearly half of all Canadian COVID-19 deaths. ³⁰ In Ontario, as of April 15, 2020, 114 of 631 Ontario LTCHs have declared COVID-19 outbreaks and 145 COVID-19-related deaths have been reported in these homes.

Given the severity of COVID-19 amongst the elderly, and the evidence of ongoing transmission with severe outcomes in LTCHs for the elderly, it is critical to develop interventions to minimize the spread of disease in this setting. As vaccines and treatment for COVID-19 remain unavailable, all possible alternative interventions must be explored. Chemoprophylaxis of at-risk individuals has been identified as an important potential control strategy.

The use of chemoprophylaxis, both pre- and post-exposure to a known case is well established for the prevention of viral infections such as influenza and human immunodeficiency virus. ³²⁻³⁴ Post-exposure chemoprophylaxis for seasonal influenza has been identified to significantly reduce incident cases in several meta-analyses, ³⁵⁻³⁷ and is a critical component of outbreak control in LTCHs. ³³ Further, observational data has indicated potential benefits for post-exposure chemoprophylaxis for another coronavirus infection, the Middle East Respiratory Syndrome. ³⁸ Another evidence-based chemoprophylaxis strategy, pre-exposure prophylaxis (PrEP), involves administering an antimicrobial agent to people at high risk before exposure has been confirmed, and is widely used for the prevention of malaria and HIV infection. ³⁴ Chemoprophylaxis is also used in the control of outbreaks of group A streptococcal infection in long term care, and in the prevention of transmission to close contacts of patients with streptococcal toxic shock syndrome. ^{39,40}

In Ontario, current recommendations are that any resident or staff member of a LTCH who develops symptoms of an upper respiratory tract infection be tested for COVID-19, and that any resident transferred to an acute care hospital with symptoms compatible with COVID-19 be tested. An outbreak is defined as the identification of a single case of COVID-19 in a LTCH; however, in some circumstances, single cases in either residents or staff have not progressed to involve additional resident or staff cases. These recommendations are intended to ensure that all cases are identified in LTCH, so that additional measures can be instituted early. Despite these measures, new outbreaks in LTCHs are being reported daily in Ontario, and most outbreaks are continuing. We expect that both individual cases of disease and already established outbreaks will be identified in many LCTHs over the coming months.

To address the need to intervene to prevent the spread of COVID-19 in long-term care facilities, we propose a cluster-randomized placebo-controlled trial of chemoprophylaxis in LTCHs experiencing COVID-19 outbreaks.

4.2 Current Treatment Options and rationale for studying Favipiravir

At the time of writing, definitive therapies for established COVID-19 remain to be defined. Significant interest exists in repurposing existing antiviral agents for use against COVID-19.

Favipiravir is a purine nucleoside analogue, which acts as a competitive inhibitor of RNA-dependant RNA polymerase. ⁴¹ It has activity against influenza A and B including activity against oseltamivir and zanamivir-resistant influenza viruses, several agents of viral hemorrhagic fever, and SARS-CoV-2 *in vitro*. ⁴¹⁻⁴³ Favipiravir is approved for novel epidemic influenza strains unresponsive to standard antiviral therapies in Japan.

Favipiravir was identified to have activity *in vitro* against SARS-CoV-2, albeit a high concentration was required as compared to chloroquine or remdesivir (EC₅₀ = $61.88 \mu M$). Despite a similarly elevated EC₅₀ identified for favipiravir and Ebola virus, it was identified in previous animal models to be highly effective as post-exposure prophylaxis for mice exposed to an Ebola virus challenges, with rapid virologic response preventing mortality. ^{44,45} Based on the

dosing strategies and pharmacokinetic data from human influenza trials, a intensified dosing strategy of 6000 mg loading on day 1 followed by 1200 mg PO BID maintenance therapy for 10 days was employed in a single-arm clinical trial for Ebola virus disease in Guinea. 46

In a retrospective analysis of 124 patients with Ebola virus disease in Sierra Leone, those treated with favipiravir had a significantly higher survival rate compared to patients receiving supportive management (56% v. 35.3%, p=0.027). Patients received favipiravir 800 mg PO BID on day 1 and 600 mg PO BID for days 3-11. Viral loads were quantified for 35 patients twice during their hospitalization and were significantly reduced amongst patients receiving favipiravir.

Favipiravir has also been used as pharmacologic post-exposure prophylaxis for Ebola virus disease. ⁴⁸ In a case series of four healthcare workers with higher risk Ebola virus exposures, including two hollow-bore needle stick injuries, none of the patients who received 10 days of high-dose favipiravir developed Ebola virus disease.

Early clinical experience with favipiravir for COVID-19 is promising. An open-label nonrandomized trial of 80 patients with COVID-19 in China identified a significant reduction in the time to SARS-CoV-2 viral clearance in patients treated with favipiravir compared to historical controls treated with lopinavir/ritonavir. Patients with mild or moderate COVID-19 were enrolled within 7 days from disease onset; those with severe or critical disease, ≥ 75 years old, chronic liver disease, or end-stage renal disease were excluded. Patients in the intervention arm received Favipiravir 1600 mg PO BID on day 1 followed by 600 mg PO BID on days 2-14. Both arms were co-treated with inhaled IFN- $\alpha 1b$ 60 μg BID and therapy was continued until viral clearance, up to a maximum of 14 days. Thirty-five patients were assigned to favipiravir and 45 patients to lopinavir/ritonavir, with a median age of 47 (IQR 35.8-61); 13.7% were ≥ 65 years old. There was a significant reduction in the median time to viral clearance with favipiravir (4 days; IQR 2.5-9) as compared to lopinavir/ritonavir (11 days; IQR 8-13; p <0.001). Further, by day 14, 91.4% of patients in the favipiravir arm had radiographic improvement versus 62.2% of the lopinavir/ritonavir arm. There was a significantly lower rate of adverse events in patients receiving favipiravir (11.4% v. 55.6%, p<0.01).

In an open-label randomized trial in China, 240 patients with confirmed COVID-19 were randomized to favipiravir or arbidol. Favipiravir was given at 1600 mg PO twice on day 1 followed by 600 mg PO BID until day 7-10. The clinical recovery rate by day 7 of treatment was higher amongst patients receiving favipiravir, albeit not achieving statistical significance (61.21% v. 51.67%, p=0.1396). Amongst patients with moderately severe disease, there was a significantly higher rate of clinical recovery by day 7 with favipiravir (71.43% v. 55.86%).

Given the demonstrated in-vitro of activity of favipiravir against SARS-CoV-2 and signals of benefit in early clinical experience for COVID-19, further studies are urgently needed. To address this need, there are several active clinical trials to assess the therapeutic efficacy for COVID-19. However, no trials to date have focused on outbreak control, an area of significant need. It is critical to evaluate the efficacy of favipiravir as chemoprophylaxis against COVID-19 using a placebo-controlled randomized trial.

As over three hundred trials are currently registered for treatment of COVID-19 in China, and in-vivo data may emerge during the conduct of this study for the therapeutic efficacy for particular pharmacotherapeutics. The study team will monitor findings from ongoing treatment trials, and if an alternative agent is identified to be more effective at study initiation,

consideration will be given to altering the study drug. Any such modification would require a formal amendment to the study protocol, regulatory approvals, and ethical approvals.

4.3 Potential Risks and Benefits to Human Participants

Overall, more than 40 clinical studies with favipiravir have been conducted globally, mainly in the US and Japan. Favipiravir has been well tolerated in studies in adults and elderly subjects with uncomplicated influenza. A consistent safety profile composed of relatively low frequencies of mild to moderate adverse events clustering around the system organ classes of gastrointestinal disorders has been characterized. Mild to moderate transient, asymptomatic elevations in serum uric acid and mild to moderate diarrhea are the two most common adverse events known to occur with favipiravir. Favipiravir has been safely studied with therapy durations up to 22 days (JP120, Phase 1 study).

Favipiravir is considered a safe drug. No related serious adverse events occurred in licensure studies of favipiravir. ⁷¹ Preclinical and animal studies show no direct suppression of white blood cell types or immunosuppression by favipiravir. Genotoxicity studies indicate that favipiravir does not pose a clinical genotoxic risk; however, based on the results of embryo-fetal toxicity studies, favipiravir is not recommended for use in pregnant females, those who may become pregnant, or those who are nursing. Though an inhibitor of CYP 2C8 and aldehyde oxidase, few drugs are contra-indicated. Overall, the safety of favipiravir suggests that the potential benefit to human participants exposed to a confirmed case of COVID-19 generally outweighs potential risks.

5. DEFINITIONS

Chemoprophylaxis

When an outbreak of COVID-19 is declared in a LTCH the state of LTCH unit residents who do not have COVID-19 can be classified into 1 of 3 categories: Category 1) not exposed and therefore not incubating (likely representing the majority of the unit residents), Category 2) exposed and incubating but with no detectable virus, Category 3) exposed, incubating with detectable virus. "Chemoprophylaxis" in this study refers to the use of a pharmacologic agent for either pre-exposure (category 1) or postexposure prophylaxis (category 2), or for pre-emptive therapy (category 3). When an outbreak is identified in a LTCH, it is difficult or impossible to assess the degree of exposure for individuals; most often many individuals have had relatively low risk exposure and it is not possible to predict which of them will develop disease. Often, several days of undetected exposure have occurred. Thus, all residents and staff should be considered as incubating and about to develop disease. The term chemoprophylaxis is therefore intended to cover all at-risk individuals in this context. Infected residents will also receive study drug. Infected staff will be excluded from work and, if possible, referred to trials of treatment.

Chemoprophylaxis period

Chemoprophylaxis for all unit residents will be started as early as a COVID-19 outbreak has been recognized at a unit (2 or more symptomatic residents with positive COVID-19 test within 7 days). Chemoprophylaxis will be continued until day 25.

Long term care home for the elderly (LTCH)

"Long-term care home" mean a resident that is licensed as a long-term care home under the Long-Term Care Homes Act, 2007. LTCHs serving older adults which are not so licensed but which have units in which medication can be delivered from a central source and adherence can be monitored are also eligible for inclusion.

Microbiologically confirmed COVID-19:

Detection of SARS-CoV-2 RNA in any patient specimen (mid-turbinate swab, nasopharyngeal swab, oropharyngeal swab, sputum specimen, endotracheal aspirate, bronchoalveolar lavage specimen, stool, blood etc.).

Outbreak in LTCH

Two or more cases of acute illness due to COVID-19 in residents on one unit, with onset within 7 days.

Rationale: In contrast to influenza which has an estimated serial interval of 2.2-2.8 days, ⁷³ COVID-19 has been identified to have a serial interval ranging from 4.4-7.5 days, justifying the use of a longer-time span between cases for the purposes of outbreak definition.

Outbreak control

Outbreak control is defined as no new cases of COVID-19 in residents for 24 consecutive days up to day 40 after the start of prophylaxis.

Rationale: The experience with oseltamivir for influenza is such that when it is given for post-exposure prophylaxis, it also has activity for pre-emptive therapy. As a result, oseltamivir

can both prevent incident cases and resolve pre-symptomatic infections, leading to a rapid termination of an outbreak with universal prophylaxis with oseltamivir. Nonetheless, pre-emptive therapy is often incompletely effective, and it is common to see new cases of influenza with onset within the first 2-4 days (one incubation period) of influenza, and occasionally, a single case occurs later.

We do not yet know if any drugs are effective for therapy of COVID-19 or pre-emptive therapy of subclinical COVID-19. It is possible that drugs may be effective for prophylaxis but not pre-emptive therapy. For COVID-19, if the therapy is effective for prophylaxis but ineffective for pre-emptive therapy, new cases may continue to be observed during the first incubation period (median 5 days, 95th percentile of 12.5 days) after prophylaxis is started. If prophylaxis is completely effective, then no cases should occur after this point. However, if individual level prophylaxis is incompletely effective, or if transmission occurs to residents or staff not able to take prophylaxis, then some transmission might occur without compromising outbreak control. Assuming that the period of infectivity is 10 days, and the maximum incubation period is 14 days, then an outbreak can be considered controlled (or ended) if no cases occur for 25 days after the day of onset in the last case.

Study Day 1

Day 1 is defined as the first day of receipt of chemoprophylaxis in the LTCH.

Symptomatic microbiologically confirmed COVID-19 disease in residents: a respiratory specimen (e.g. nasopharyngeal swab) yielding SARS-CoV-2 RNA in association with new onset fever (≥37.8°C) OR cough OR one or more of the following other respiratory or systemic symptoms (fatigue, myalgias, arthralgias, shortness of breath, sore throat, chills, loss of appetite, vomiting or diarrhea, change in level of responsiveness or capacity for activities of daily living (ADL)), OR requirement for hospitalization OR death.

Symptomatic microbiologically confirmed COVID-19 disease in staff: fever (≥38.0°C or cough or two or more of the following other respiratory or systemic symptoms (fatigue, myalgias, arthralgias, shortness of breath, sore throat, chills, loss of appetite, anosmia, vomiting or diarrhea).

Unit

A unit is the section of the LTCH experiencing an outbreak which will be randomized to study drug. Units are sections within the LTCH which have a nursing station and shower room and on which residents and most staff can be reliably physically separated from residents of other units for the duration of the outbreak. Units with >32 residents will be excluded.

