1) Choose LTCH institutions for inclusion in the study for COVID19 screening 2) Identify Units with COVID19 outbreak (>=2 symptomatic and positive tested residents within a week) 3) Assess outbreak units for inclusion / exclusion. If qualifies-randomize unit to favipiravir or placebo (N=16 units) LTAC Institution 1 LTAC Institution 2 LTAC Institution 3 LTAC Institution 4 LTAC Institution 5 ITAC Institution 6 Unit 1 Unit 2 Unit 3 Unit 4 Unit 5 Unit 6 LTAC Institution 7 LTAC Institution 10 LTAC Institution 12 LTAC Institution 8 LTAC Institution 9 LTAC Institution 11 Unit 1 Unit 2 Unit 3 Unit 4 Unit 5 Unit 6 placebo favipiravir Unit 4 Unit 5 Unit 6 Unit 7 Unit 8 Unit 1 Unit 2 Unit 3 Unit 4 Unit 5 Unit 6 Unit 7 Unit 8 Unit 1 Unit 2 Unit 3 4) Chemoprophylaxis is continued for 25 days 5) On day 40 (15 days after end of prophylaxis): for each unit, determine control of the outbreak

Figure 1: a scheme of study flow.

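### The primary endpoint does not say where its 24 case-free days must fall, so the same unit can be controlled or not controlled, and its rationale gives 25 days instead of 24

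*Protocol*

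**What the plan says.** Section 5 (Outbreak control) defines control as "no new cases of COVID-19 in residents for 24 consecutive days up to day 40 after the start of prophylaxis". The Synopsis and Section 6.4 use the same rule. Sections 6.1 and 15.3.1 also require 24 consecutive days up to day 40. Section 6.1 does not limit the cases to residents, and Section 15.3.1 refers to cases in the facility. None of the five places says that the run must end on day 40, or how a case that follows a completed run is counted.

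The clock and the treatment period are clear. "Day 1 is defined as the first day of receipt of chemoprophylaxis in the LTCH", and "Chemoprophylaxis will be continued until day 25". The study scheme in Section 6.1 places the judgement later: "On day 40 (15 days after end of prophylaxis): for each unit, determine control of the outbreak".

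The rationale in Section 5 derives the length of the case-free period: "Assuming that the period of infectivity is 10 days, and the maximum incubation period is 14 days", it concludes that "an outbreak can be considered controlled (or ended) if no cases occur for 25 days after the day of onset in the last case".

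**The concern.** The phrase can mean any 24-day run completed by day 40, or the 24 days that end on day 40. Under the first meaning, a unit with no case on days 1-24 has met the endpoint before prophylaxis is over, and nothing on days 25-40 can change that. Under the second, the 15 days after the drug stops always count.

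The pattern that separates the two is an early quiet period followed by cases. A suppressive drug withdrawn on day 25 could plausibly produce it. The endpoint is one yes/no result per unit and there are 16 units, so the choice of reading can decide the primary test. It should not be left open until the data are in.

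The 24 and 25 days are a smaller problem of the same kind: the stated reason for the endpoint does not give the endpoint's own number.

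**Working it through.** **The plan's own figure.** Section 15.2 claims more than 85% power for 8 vs 8 units, 12.5% vs 87.5% controlled, two-sided Fisher's exact test at 0.05. Summing the binomial probabilities of all outcomes with p ≤ 0.05 gives 87.0%, so the claim reproduces. It does not depend on the point here until the control rates under each reading are known.

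**Windows.** A 24-day run within days 1-40 can start on any day from 1 to 40 − 24 + 1 = 17, which gives 17 possible windows. Tied to day 40, only one remains: days 17-40. It contains the post-prophylaxis days 26-40. Every unit that passes on days 17-40 also passes under the any-run reading, so the literal reading can only add controlled units.

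**Which rebounds are ignored.** Let e be the day of the last early case and R the day of the first rebound case. The any-run rule is met before the rebound if days e+1 to e+24 are free of cases, that is, if R ≥ e + 25. With no early case, the condition is R ≥ 25.

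| Case days | Any 24-day run | Days 17-40 |
|---|---|---|
| 26, 28, 30, 35 | controlled | not controlled |
| 5, 30, 33, 36 | controlled | not controlled |
| 12, 37, 39 | controlled | not controlled |
| 10, 25 | not controlled | not controlled |
| 16 only | controlled | controlled |
| 17 only | not controlled | not controlled |

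**Count over a grid.** Take e as none or day 1 to 16 (17 values) and R as day 26 to 40 (15 values): 17 × 15 = 255 combinations. With no early case all 15 pass under the any-run reading. With e = 1, 2, ..., 15 the numbers passing are 15, 14, ..., 1, which sum to 120, and with e = 16 none passes. The total is 15 + 120 = 135 of 255. Under days 17-40 none passes. This is a count of patterns, not a probability.

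**24 or 25 days.** The rationale's components give 10 + 14 = 24. With 25 days the window ending on day 40 would be days 16-40. A unit whose only case is on day 16 is controlled with 24 days and not controlled with 25.

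**Effect of one favipiravir unit on the test** (two-sided Fisher, 8 per arm, favipiravir vs placebo; both margins are symmetric, so the two tails are equal):

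- 7/8 vs 1/8: 2 × (64 + 1) / 12,870 = 0.010
- 6/8 vs 1/8: 2 × (224 + 8) / 11,440 = 0.041
- 5/8 vs 1/8: 2 × (448 + 28) / 8,008 = 0.119

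Losing one favipiravir unit from 6/8 removes significance. Losing one from the planned 7/8 does not.

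**The case against.** The strongest reply is that the phrase already means the 24 days running up to day 40. Two places support this. The scheme determines control on day 40, and the rationale counts from onset in the last case, so a unit with cases on days 26-35 would fail the rationale. This stands as evidence of intent. It does not settle the matter, because no statement of the endpoint says so and the literal words allow the other reading.

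A reader might infer that every unit that rebounds after day 25 counts as controlled. The documents do not support that, even on the literal reading. Section 5 itself expects early cases from infections already incubating (median 5 days, 95th percentile 12.5 days). After a last early case on day 5, 10 or 12, only a rebound from day 30, 35 or 37 on is ignored.

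A reader might also infer that the endpoint is biased towards favipiravir by some stated amount. The pattern that is forgiven is early suppression followed by rebound, but the protocol gives no rebound rate, no rate of new introductions and no individual-level protection for favipiravir. Any modelled percentage would rest on outside inputs, and a placebo unit could show the pattern too.

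Finally, the four-day tolerance around the day-40 visit might be read as leaving the last days of the window unobserved. The protocol provides daily assessment by home staff, faxed line lists and chart review at day 40. An early swab therefore affects only screening for infections without symptoms, and rules for dating such cases can properly sit in an analysis plan.

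**Conclusion.** The point holds as an ambiguity in the primary endpoint that can give different primary results from the same data, together with a one-day contradiction in its rationale. It is not shown that the sponsor intended the any-run rule.

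The size of the effect is unknown. What can be said from the documents is that the readings disagree on 135 of the 255 patterns enumerated, always in the direction of more units counted as controlled under the literal reading. One favipiravir unit is enough to change significance at 6/8 vs 1/8, though not at the planned 7/8 vs 1/8. The day counts rest only on day 1 as first dose and day 40 as the last day counted.

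It belongs in the protocol and not only in an analysis plan, because the protocol itself states the endpoint in five places and leaves the window open in all of them.

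**What to change.** In the Synopsis, Section 5, Section 6.1, Section 6.4 and Section 15.3.1, define control in one identical sentence: no new microbiologically confirmed case of COVID-19 in a resident of the randomised unit on study days 17 to 40 inclusive. This also removes the differences over whose cases count. In the Section 5 rationale, make the 24 and 25 days agree; the rationale's own sum and every statement of the endpoint give 24.

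The cost is protocol wording, with no extra visits or swabs. The one downside is that a late new introduction after a long quiet period counts as failure. Reporting the any-run version as a sensitivity analysis would show whether this matters.
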